## **5. Inclusion/Exclusion Criteria**

Eligibility criteria include (a) participation in the Addictions Treatment Program at the Truman VA, (b) DSM-5 criteria for moderate to severe Alcohol Use Disorder, (c) alcohol use in the past 2 months at baseline, and (d) the DSM-5 episodic criterion (duration at least 1 month) for Insomnia Disorder.

Participants will be excluded if they are unable to provide informed consent, demonstrate cognitive impairment (Mini Mental Status Exam score <26), report a manic episode or seizure in the past year (contraindications for CBT-I), have a severe psychiatric disorder that requires immediate clinical attention (e.g., psychosis, suicidal ideation with intent and plan), or began a sleep medication in the past 6 weeks. Consistent with standard practice, those who endorse symptoms of sleep-related breathing disorders ( $\geq 2/8$  symptoms on the STOP-BANG), restless leg syndrome, periodic limb movement disorder, or narcolepsy will be referred for polysomnography.

## **6. Drugs/ Substances/Devices**

N/A

## **7. Study Statistics**

*Outcome measures.* Outcome measures are listed in Table 1 above. Primary outcomes include recruitment, retention, and treatment satisfaction (Aim 1) as well as insomnia severity, total wake time, sleep quality, percent days abstinent, percent heavy-drinking days, alcohol problems, and use of alcohol or other drugs as a sleep aid (Aim 2). Secondary (Aim 3) outcomes include treatment-related learning, executive function (attention, working memory, delayed discounting, impulsivity), negative affect, emotion regulation, craving, and mental health symptoms (PTSD, depression, anxiety, life satisfaction).

*Aim 1 analyses.* Recruitment (goal  $\geq 4$  pts/mo) and retention rates ( $\geq 70\%$  complete 5/5 sessions) will indicate feasibility of the intervention. Treatment satisfaction (average score  $\geq 3$ , indicating ‘good’ quality) will serve as an indicator of acceptability. Recruitment, retention, and satisfaction will be measured separately for insomnia and alcohol treatments. We do not expect group differences in recruitment. Descriptive statistics, chi-square, and t-tests will be used to determine between-group differences in retention and satisfaction.

*Aims 2-3 analyses.* Cohen’s  $d$  (adjusted for baseline scores) and 95% CIs will be used to examine the magnitude of between-group differences at post-treatment and 6-week follow-up. We will use HLM to compare conditions at post-treatment and 6 weeks. We chose HLM over other statistical approaches (e.g., ANOVA) because it requires fewer assumptions, has superior ability to handle missing data, and will yield greater

statistical power. In each model, the Level 1 variable will be time. Level 2 portions of the model will include the effect of condition. Hypotheses will be tested by regressing condition on the Level 1 intercept and time effect. Analyses will be intent-to-treat. We will examine whether attrition is associated with any baseline variables and control for such variables when necessary.

*Power analysis.* Post-hoc power analyses conducted in G\*Power 3.0.10 indicate that 80 participants will provide strong power ( $1 - \beta = .99$ ) to detect within-between interactions of moderate magnitude ( $f = .25$ ).

*Early stopping rules.* PI [name] will monitor adherence to the study protocol and adverse events on an ongoing basis and discuss these issues with the research team during weekly meetings. All serious and unexpected adverse events will be reported to the IRB within 24 hours of receipt of information. Other adverse or potentially adverse events will be monitored and reported at annual continuing reviews. After discussion with the IRB, we will discontinue the trial if there is (a) compelling evidence from this or another study of a serious adverse effect of CBT-I that has potential to override potential benefit, (b) compelling evidence from this or another study of a significant beneficial effect of CBT-I, such that continued denial to other groups would be unethical, or (c) low probability of addressing study aims within a feasible time frame.

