Consistent with PA-18-202, the proposed R21 aims to examine the feasibility, acceptability, and initial efficacy of a CBT-I supplement to outpatient alcohol treatment. The **primary objective** of this study is to enhance alcohol treatment to account for the unique needs of Veterans with sleep disorders. We propose a 6-week randomized trial, in which 80 Veterans will be randomly assigned to receive Cognitive Behavioral Therapy for Insomnia (CBT-I) or minimal treatment (sleep hygiene only; SH) in addition to treatment as usual. Individuals participating in the Addictions Treatment Program at the Truman VA will be eligible to participate if they meet DSM-5 criteria for AUD and the episodic criterion ( $\geq 1$  mo) for Insomnia Disorder. Participants will complete assessments at baseline, post-treatment, and 6-week follow-up. We propose the following specific aims:

**Aim 1: To test the feasibility and acceptability of CBT-I delivered concurrently with alcohol treatment.** Recruitment (anticipated enrollment of at least 2 Veterans per month) and retention rates (goal  $\geq 70\%$  complete 6/6 treatment sessions) will indicate feasibility of the intervention. Treatment satisfaction (average score  $\geq 3$ , indicating ‘mostly satisfied’) will serve as an indicator of acceptability. Retention and satisfaction will be measured separately for insomnia and alcohol treatments.

**Aim 2: To evaluate the initial efficacy of CBT-I on insomnia and alcohol use outcomes.** We hypothesize that Veterans receiving CBT-I will demonstrate greater improvements in insomnia severity, sleep efficiency, use of alcohol as a sleep aid, percentage of heavy-drinking days, and alcohol-related problems post-treatment and at 6-week follow-up.

**Aim 3 (exploratory): To examine proximal intervention outcomes.** We hypothesize that Veterans receiving CBT-I will demonstrate greater post-treatment improvements in attention (vigilance), working memory, treatment-related learning, negative affect, and emotion regulation.

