#### 4. Study Procedures

This study will examine the feasibility, acceptability, and initial efficacy of Cognitive Behavioral Therapy for Insomnia (CBT-I) delivered concurrently with CBT for AUD using a randomized, parallel, two-group design (see Figure 1). Eighty Veterans will be randomly assigned to either **CBT-I** or a sleep hygiene education control (**SH**). All outcomes will be assessed at baseline, post-treatment, and 6-week follow-up. This design will allow us to test the feasibility and acceptability of CBT-I among those in treatment for AUD (**Aim 1**); evaluate the initial efficacy of CBT-I in improving insomnia and alcohol-related outcomes (**Aim 2**); and examine CBT-I effects on attention, working memory, learning, negative affect, and emotion regulation, which may be examined as mediators in a subsequent trial (**Aim 3**).

**Study site.** Participants will be recruited through the Addictions Treatment Program at the Harry S. Truman Memorial Veterans Hospital (Truman VA) in Columbia, MO. We will recruit 115 participants over 20 months (see Table 2) to obtain a final sample of at least 80 participants.

[figure not shown]

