Participants will also receive reminder texts/calls, have access to free parking, and receive treatment at no cost.

*Cognitive Behavioral Therapy for Insomnia (CBT-I).* CBT-I will be delivered individually, in person, in five weekly one-hour sessions. A sixth week of treatment will be included – and scheduled for the same date as the post-treatment assessment – if the participant and research team agree that it would be beneficial (e.g., if a participant has difficulty grasping cognitive therapy concepts). Study therapists will follow the 2014 CBT-I in Veterans manual developed by leading researchers in the behavioral sleep medicine field (see Table 3). Intervention components include (1) sleep hygiene: limiting naps; avoiding caffeine, tobacco, alcohol, and rich/heavy foods before bedtime; exercising; establishing a bedtime routine; and creating a comfortable sleep

Table 1. *Assessment, therapy, and payment schedule*

Week	Assmt	CBT-I	Paymt	Bonus
1	BL		10	
2		S1	20	10
3		S2		
4		S3		
5		S4		
6		S5		
7	Post-tx	(S6)	40	
8				10
9				
10				
11				
12	1mo		50	
13				10

*Note.* 1mo = 1 month. Assmt = assessment. BL = baseline. Bonus = bonus payment for completion of all 7 daily surveys. Paymt = standard payment. Tx = treatment.

environment; (2) sleep restriction: limiting time in bed in order to improve sleep efficiency, or the percentage of time in bed that is actually spent sleeping; time in bed will be titrated each week based on sleep efficiency; (3) stimulus control: strengthening association between bedroom and sleep to decrease conditioned arousal; (4) relaxation: diaphragmatic breathing, progressive muscle relaxation, and visual imagery to reduce arousal; and (5) cognitive therapy: identifying and challenging thoughts that interfere with sleep.

*Sleep hygiene (SH).* All participants will receive a one-page handout on sleep hygiene. This is the only intervention that participants assigned to the SH condition will receive and is consistent with what may be expected as standard care in a doctor's visit with a primary care physician.

Table 2. Survey Instruments and Schedule of Administration

Use	Construct	Measure(s)	Cut-score		
Use	Construct	Measure(s)	BL	Post	6wk
Screen	Insomnia severity , past 2 weeks	Insomnia Severity Index (Morin et al., 2011)		≤ 9 excluded at phone screen	
	Sleep apnea , past month	STOP questionnaire (Chung et al., 2008)		≥ 3 excluded at phone screen	

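### The Aim 1 feasibility thresholds are not consistent: retention is 6/6 sessions in two places and 5/5 in Section 7 although the sixth session is optional, and two monthly recruitment goals are left unreconciled

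*Combined protocol and SAP*

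**What the plan says.** Section 7 (Study Statistics) lists recruitment, retention and treatment satisfaction as the Aim 1 primary outcomes.

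**Retention.** The threshold is 70% throughout, but what must be completed differs:

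- Section 7, Aim 1 analyses: "complete 5/5 sessions) will indicate feasibility of the intervention".
- Section 3 (Background), Aim 1: "complete 6/6 treatment sessions) will indicate feasibility of the intervention".
- Section 4, Table 2, retention row: six of six, and the row names CBT-I sessions.
- Section 4, CBT-I description: "CBT-I will be delivered individually, in person, in five weekly one-hour sessions". A sixth is added only when participant and team agree that it would help. Table 1 prints it in brackets.

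**Recruitment.** Three statements bear on it:

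- Section 3, Aim 1: "Recruitment (anticipated enrollment of at least 2 Veterans per month".
- Section 7: a goal of at least 4 per month.
- Section 4, Table 2, recruitment row: attendance at one or more CBT-I sessions.

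The accrual plan in Section 4 reads "We will recruit 115 participants over 20 months", in order "to obtain a final sample of at least 80 participants". The sleep hygiene (SH) arm receives a handout and no CBT-I sessions.

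**The concern.** These rates are what the plan will use to call the intervention feasible, and feasibility is the first stated objective. If the numerator changes between sections, the feasibility conclusion can turn on which section is applied, and that choice could be made once the data are known.

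The retention conflict is more than a difference of one session. The sixth session is not offered to everyone; the example given for using it is a participant who has trouble with the cognitive therapy material. A literal 6/6 rule therefore measures how often the optional session is used as well as attendance, and it counts against participants who did not need it.

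For recruitment, two monthly goals that differ by a factor of two stand beside a table definition that is tied to neither of them.

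**Working it through.** **Inputs.** 80 randomised to two arms, 115 to be recruited and 20 months (Section 4); 70% retention goal (Sections 3 and 7); recruitment goals of 2 per month (Section 3) and 4 per month (Section 7). Assumption: 1:1 allocation, so 80/2 = 40 in CBT-I. The documents do not state the ratio.

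**The plan's own accrual figures.** 80/0.70 = 114.3, rounded up to 115. This reproduces the recruitment target if 30% loss is assumed; the documents give no loss rate, and 30% is the complement of the retention goal. As monthly rates, 115/20 = 5.75 and 80/20 = 4.0.

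**Retention.** The pass mark is 0.70 × 40 = 28 participants. Let *a* be the number who complete the five scheduled sessions and *b* the number of those who also complete a sixth. Then the 5/5 rate is *a*/40 and the 6/6 rate is *b*/40. Since *b* cannot exceed the number who have the optional session, neither can the 6/6 numerator.

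With perfect attendance (*a* = 40), the 5/5 rate is 40/40 = 100%. The 6/6 rate depends only on how many have the optional session, so a range is shown:

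| Have the optional session | 6/6 rate | 70% goal |
|---|---|---|
| 10 of 40 | 25% | missed |
| 20 of 40 | 50% | missed |
| 27 of 40 | 67.5% | missed |
| 28 of 40 | 70% | met |

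With imperfect attendance the demand is steeper. If *a* = 34, the 5/5 rate is 34/40 = 85%, and 6/6 needs 28/34 = 82% of those completers to complete a sixth session as well.

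As probabilities, take X ~ Binomial(40, p) and P(X ≥ 28), with an assumed 80% chance of completing five sessions:

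- 5/5 rule, p = 0.80: 0.957.
- 6/6 rule, 90% of completers have a sixth, p = 0.72: 0.684.
- 6/6 rule, 75% have a sixth, p = 0.60: 0.129.
- 6/6 rule, 50% have a sixth, p = 0.40: 0.000 to three decimals.

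**Recruitment.** 2 × 20 = 40 and 4 × 20 = 80. If both goals count the same people, any 20-month total from 40 to 79 meets Section 3 and misses Section 7. If the lower goal counts CBT-I starters and the higher one both arms, they agree at 1:1, because 4 × 1/2 = 2. Table 2 does not settle which is meant: starting CBT-I is not the same as enrolment (Section 3), and SH participants cannot meet that definition, so it cannot yield a two-arm count. The 5.75 per month needed to recruit 115 matches neither goal.

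**The case against.** **On retention**, the best defence is that the intent can be recovered. The statistics section says 5/5, and that agrees with the treatment description and with the bracketed session in Table 1. The 6/6 wording sits in proposal-style aims text and one table row, so an analyst who follows Section 7 would not penalise a missing optional session. This has weight, and it limits the severity. It does not remove the conflict: no section is said to prevail, and nothing defines 6/6 as all sessions offered. Nor can 6/6 be assigned to the alcohol treatment on the strength of "Retention and satisfaction will be measured separately for insomnia and alcohol treatments", because Table 2 attaches it to CBT-I by name.

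**On recruitment**, a reader might infer that the plan never says who is counted, or that the two goals flatly contradict each other. The documents support neither. Table 2 does give a counting rule, and 2 and 4 per month fit 40 CBT-I starters and 80 overall at an assumed 1:1 split. What stands is narrower: no section states that reconciliation, Section 3 speaks of enrolment without naming an arm, and neither goal refers to the Table 2 rule.

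**On consequence**, this is a pilot. No go/no-go rule is attached to the thresholds, and the early stopping criterion on achieving the aims in a feasible time cites no number. Raw attendance and accrual can be reported whichever rule is used. The optional-session shares in the working are illustrations, not predictions.

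**Conclusion.** The retention definition is wrong as written and should be fixed. A primary outcome has two live definitions, and under the literal 6/6 version full attendance at the scheduled sessions can still be scored as failure. The firm result is the ceiling: the 6/6 rate cannot exceed the share who have the optional session, so at 40 in CBT-I the goal is out of reach unless at least 28 have it, even when 5/5 retention is 100%. That count rests on 1:1 allocation; the ceiling itself does not. The actual share is unknown.

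The recruitment goals are unreconciled rather than shown to be contradictory. Their size is 40 against 80 over 20 months.

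A reader might also infer that the trial will fall short of its sample or that its efficacy results are compromised. The documents do not support this: 4 per month for 20 months gives exactly the planned final sample of 80, and the Aim 2 and Aim 3 analyses and the sample size do not use these thresholds.

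**What to change.** (a) Reconcile the session count across Aim 1 in Section 3, the CBT-I description and Table 2 in Section 4, and Section 7. Then define CBT-I retention once, against the sessions scheduled for every CBT-I participant, so that not having the optional session is not a failure. The number of sessions is for the sponsor to settle.

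(b) State one recruitment goal and the population it counts, identically in Aim 1, Table 2 and Section 7. For orientation, 4 per month corresponds to the final sample of 80 in 20 months. Report attendance at one or more CBT-I sessions separately, as treatment initiation.

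Both should be settled before the feasibility results are examined. The cost is wording in those four places, with no change to sample size, data collection or the efficacy analyses.

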Use	Construct	Measure(s)	BL	Post	6wk
Cov	Demographics	See instruments	X		
	Other drug use , past 6 weeks	Drug Use Screening Inventory	X	X	X
	Use of sleep medication	Daily Sleep Diary (Carney et al., 2012)	X	X	X
Aim 1	Recruitment	Completion of ≥ 1 session of CBT-I		X	
	Retention	Completion of 6/6 sessions of CBT-I		X	
	Treatment satisfaction , measured separately for CBT-I and CBT-AUD	Client Satisfaction Questionnaire (Larsen et al., 1979)			X
Aim 2	% abstinent days , past 6 weeks	Timeline Follow-back (TLFB) for alcohol (Sobell & Sobell, 1996)	X	X	X
	% heavy-drinking days (≥4/5 drinks/day for women/men)				
	Alcohol problems , past 6 weeks	Short Inventory of Problems ([name] et al., 1995)	X	X	X
	Use of alcohol or other drugs to help with sleep , past 6 weeks	Daily Sleep Diary (Carney et al., 2012)	X	X	X
	Insomnia severity , past 2 weeks	Insomnia Severity Index (Morin et al., 2011)	X	X	X
	Total wake time , average past week	Daily Sleep Diary (Carney et al., 2012)	X	X	X
	Sleep quality , average past week	Daily Sleep Diary (Carney et al., 2012)	X	X	X
	Dysfunctional beliefs, past month	Dysfunctional Beliefs about Sleep Scale	X	X	X
Aim 3	Treatment-related learning	Project SAVE Alcohol Quiz Project SAVE Alcohol Vignette	X	X	X
	Executive functioning	Psychomotor Vigilance Task (Dinges et al., 1985) N-back Task (Schmiedek et al., 2014) Monetary Choice Questionnaire UPPS Measure of Impulsivity Cognitive Failures Questionnaire	X	X	X
	Negative affect , past week	Positive and Negative Affect Schedule	X	X	X
	Emotion regulation , past 30 days	Brief Difficulties in Emotion Regulation Scale (Bjureberg et al., 2016)	X	X	X
	Alcohol craving , past week	Penn Alcohol Craving Scale	X	X	X
	Mental health symptoms	PTSD Checklist for DSM-5 Patient Health Questionnaire-9 for depression GAD-7 measure of anxiety Satisfaction with Life Scale	X	X	X

*Note.* BL=baseline. Cov = potential covariates. Post = post treatment. Wk = week.

*Blinding.* PI [name] will not be blinded to block size or participant assignment because she will inform study therapists of participant assignment to conditions. However, PI [name] and study therapists will be blinded to assessment outcomes, and the assessment RA will be blinded to participant condition.

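### The planned between-arm test of retention has no usable outcome: the only defined measure is CBT-I session completion, which is 0% by design in the sleep hygiene arm, and alcohol-treatment retention is promised but not defined

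*Combined protocol and SAP*

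**What the plan says.** Section 7 lists recruitment, retention and treatment satisfaction as primary outcomes for Aim 1. For the analysis it says: "Descriptive statistics, chi-square, and t-tests will be used to determine between-group differences in retention and satisfaction". It anticipates no difference between the arms in recruitment.

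The operational definitions are in Table 2 (Section 4):

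- Recruitment: "Completion of ≥ 1 session of CBT-I".
- Retention: "Completion of 6/6 sessions of CBT-I". Section 7 itself counts 5/5 sessions.
- Satisfaction: the Client Satisfaction Questionnaire, "measured separately for CBT-I and CBT-AUD".

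Of the one-page sleep hygiene handout, Section 4 says: "This is the only intervention that participants assigned to the SH condition will receive". Both arms also receive their usual alcohol treatment (Abstract; Section 3).

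The plan does intend to look at the two treatments separately. Section 3 says: "Retention and satisfaction will be measured separately for insomnia and alcohol treatments". Section 7 says: "Recruitment, retention, and satisfaction will be measured separately for insomnia and alcohol treatments".

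**The concern.** A between-arm test needs an outcome that can vary in both arms. CBT-I session completion cannot: SH participants are offered no sessions, and their referral for CBT-I comes only after the study ends. A tiny p-value would then reflect the design and say nothing about whether one arm held its participants better.

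The recruitment definition has the same flaw in milder form. If recruitment means attending a CBT-I session, the SH arm is at 0%, and a difference that Section 7 says it does not expect is guaranteed.

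The useful comparison is retention in alcohol treatment. Aim 1 concerns CBT-I given alongside that treatment, so a reader will want to know whether adding CBT-I supports attendance there or crowds it out. If the plan is followed exactly as written, nothing is specified that would answer this.

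**Working it through.** **The plan's own figure.** Section 7 gives one power figure: .99 for a within-between interaction of f = .25 with 80 participants. Alpha, the number of measurements and the correlation are not stated. Assuming alpha 0.05, correlation 0.5 and two measurements, lambda = f² × N × m/(1 − rho) = 0.0625 × 80 × 2/0.5 = 20 on 1 and 78 df, and power is 0.993. With three measurements lambda is 30 on 2 and 156 df, and power is 0.999. The figure is reproducible under these assumptions, but it concerns Aims 2-3. No calculation is given for the Aim 1 tests.

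**What each arm can show on each outcome.**

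| Outcome | CBT-I arm | SH arm | Defined in the plan? |
|---|---|---|---|
| CBT-I session completion | yes | 0% by design | yes (Table 2) |
| Recruitment as at least one CBT-I session | yes | 0% by design | yes (Table 2) |
| CBT-I satisfaction | yes | no CBT-I to rate | yes (Table 2) |
| CBT-AUD satisfaction | yes | yes | yes (Table 2) |
| Alcohol-treatment retention | yes | yes | promised only |

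For the last row, Table 2 has no attendance item, Table 1 has a session column for CBT-I only, and Section 12 mentions audio and outcome data but no program attendance records.

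**The retention test on the defined measure.** Inputs: 80 participants (Section 4), taken as 40 per arm because the allocation ratio is not stated, and the 70% completion goal (Sections 3 and 7). With x completers of 40 against 0 of 40, the Pearson statistic reduces to

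chi-square = 80 × (40x)² / [40 × 40 × x × (80 − x)] = 80x/(80 − x).

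- At the 70% goal, x = 28: 2240/52 = 43.1, p about 5e-11.
- At 15% completion, x = 6: 480/74 = 6.49, p = 0.011 (continuity-corrected 0.034, Fisher 0.026).

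So the test is significant even when completion is far below the feasibility goal. The choice between five and six sessions does not alter this, because the SH arm is at zero either way.

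**The informative quantity.** The single-arm proportion 28/40 = 70% has Wilson centre (0.70 + 3.84/80)/(1 + 3.84/40) = 0.682 and half-width 0.137, so the 95% CI is 55% to 82%. The exact interval is 53% to 83%.

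**What an alcohol-treatment comparison could show.** The documents give no retention rate for the alcohol program, so a range of control rates is assumed. With n = 40 per arm, two-sided alpha 0.05, control rate p1, CBT-I-arm rate p2, difference d = p2 − p1 and mean rate p̄:

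power = Φ{[√n × d − 1.960 × √(2p̄(1 − p̄))] / √(p1(1 − p1) + p2(1 − p2))}.

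| Assumed control rate | Power, +10 points | Power, +20 points | Detectable with 80% power |
|---|---|---|---|
| 40% | 14.3% | 43.1% | 30.7 points |
| 50% | 14.3% | 44.5% | 29.5 points |
| 60% | 15.2% | 49.7% | 27.3 points |
| 70% | 17.5% | 61.2% | 23.8 points |
| 80% | 23.7% | not applicable | 19.0 points |

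For CBT-AUD satisfaction the detectable standardised difference is (1.960 + 0.842) × √(2/40) = 0.63, before any loss to follow-up.

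**The case against.** The best defence is that the plan never says the chi-square will set CBT-I completion against zero. The sentence about measuring the two treatments separately comes shortly before the test sentence, so the tests may be meant for the alcohol-treatment versions. That reading is fair, and on it 28/40 against 0/40 only illustrates the sole defined measure. It does not rescue the plan, because the version that could be tested has no definition. Retention could also mean completing assessments, since Section 4 uses the word for follow-up incentives. But Table 2 and both stated goals count treatment sessions.

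A reader might infer stronger claims that the documents do not support:

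- That the satisfaction test is empty too. It is not: satisfaction is a questionnaire score, both arms receive alcohol treatment, and the CBT-AUD comparison is valid.
- That alcohol-treatment retention was never planned. Sections 3 and 7 both commit to it; what is missing is the operational detail. Figure 1 is not available in the text reviewed, so the statement that nothing defines it rests on the text and tables.
- That the feasibility criterion fails. The 70% benchmark is a CBT-I-arm quantity and needs no between-arm test.
- That a drinking difference could not be interpreted. The intent-to-treat comparison of CBT-I with SH, each added to usual care, stands. Attendance arises after randomisation and would help explain an effect, but it is not needed to estimate one.
- That recruitment will be tested wrongly. Section 7 names no recruitment test; Table 2's definition simply conflicts with the expectation of no difference.

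**Conclusion.** The point holds for retention and should be fixed. A named primary outcome is assigned a between-arm test, and its only defined measure is structurally zero in one arm. At 40 per arm (assumed), the test is significant both at the 70% goal (chi-square 43.1) and at 15% completion (p = 0.011), so it carries no information about differential retention. The one meaningful between-arm comparison, retention in alcohol treatment, is promised without a measure, source, window or completion rule. Table 2's recruitment definition contradicts Section 7's expectation of no group difference. For satisfaction the flaw is confined to the CBT-I score.

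The structural zero follows directly from the documents. The chi-square values depend on 40 per arm, and the power figures also depend on the assumed control rates.

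**What to change.** In Section 7 and Table 2:

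1. Report CBT-I session completion and CBT-I satisfaction for the CBT-I arm only, with 95% CIs and no between-arm test.
2. Define recruitment by enrolment or randomisation.
3. Add an alcohol-treatment retention measure for both arms, taken from the program's existing attendance records, with a stated time window and completion rule.
4. Limit between-arm comparisons to alcohol-treatment retention and CBT-AUD satisfaction. Report each as a difference with a 95% CI, which suits a pilot focused on effect sizes, and state that 40 per arm (assumed) detects only about 19 to 31 points in retention with 80% power for control rates of 40% to 80%.

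The session count in the retention definition (six in Section 3 and Table 2, five in Section 7) must be reconciled separately.

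The cost is amended wording, staff time to abstract attendance for about 80 people, and consent or authorisation language to cover it. The plan gives up one between-arm test and gains a comparison that will be imprecise. Level of care and reason for discharge could be collected as well, but the fix does not depend on them.

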### 1. Abstract

Alcohol use disorders (AUDs) are prevalent among Veterans and result in significant physical and psychological burden. Among those who receive treatment for AUDs, 1 in 3 relapses to problematic drinking within one year of treatment. Thus, additional strategies are needed to enhance alcohol treatment outcomes. One promising approach involves providing concurrent treatment for a common complaint – difficulty falling or staying asleep. Up to 74% of Veterans seeking treatment for AUD report co-occurring symptoms of insomnia. Given the negative impact of insomnia on attention and emotion regulation, insomnia symptoms may decrease patients' abilities to attend to alcohol treatment and manage negative emotions that lead to craving and relapse. Moreover, approximately 50% of individuals with AUDs report using alcohol to help them sleep, making relapse more likely for those with no other tools or skills to help them sleep. Indeed, sleep disturbance has been identified as a risk factor for relapse among individuals in alcohol treatment. Thus, effective treatment of sleep problems may enhance alcohol treatment. Cognitive Behavioral Therapy for Insomnia (CBT-I) has been effective in reducing insomnia severity in individuals with AUDs; however, no investigations have examined the efficacy of CBT-I delivered concurrently with AUD treatment to determine its impact on treatment outcomes. This R21 aims to examine the feasibility, acceptability, and initial efficacy of a CBT-I supplement to outpatient alcohol treatment. A randomized pilot trial with 80 Veterans who meet diagnostic criteria for AUD and Insomnia Disorder will be conducted. Participants will be randomly assigned to receive Cognitive Behavioral Therapy for Insomnia (CBT-I) or minimal treatment (sleep hygiene handout only; SH) in addition to alcohol treatment as usual. Outcomes will be assessed at the end of the active intervention period (6 weeks) and 6 weeks post-intervention. Outcomes of interest include recruitment/retention rates, treatment satisfaction, insomnia severity, use of alcohol as a sleep aid, percentage of heavy-drinking days, and alcohol-related problems. Analyses will focus on size of treatment effects. This study will provide initial evidence that treatment of insomnia not only improves sleep but also allows participants to derive greater benefit from outpatient alcohol treatment.

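### The HLM tests for Aims 2-3 should be baseline-adjusted condition contrasts at post-treatment and at 6 weeks, with Cohen's d taken from the same contrasts

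*Combined protocol and SAP*

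**What the plan says.** Section 7 (Study Statistics, Aims 2-3 analyses) sets the target: "We will use HLM to compare conditions at post-treatment and 6 weeks". This matches Aim 2 in section 3, which states its hypotheses for both occasions: "alcohol-related problems post-treatment and at 6-week follow-up".

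The model is then described in three steps. For Level 1: "In each model, the Level 1 variable will be time". Level 2 names condition and nothing else. For the tests: "Hypotheses will be tested by regressing condition on the Level 1 intercept and time effect".

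Baseline scores are mentioned for the effect size only. Of Cohen's d, the section says "adjusted for baseline scores) and 95% CIs will be used to examine the magnitude of between-group differences at post-treatment and 6-week follow-up". The only covariates foreseen for the models are baseline variables found to be associated with attrition; the plan will "control for such variables when necessary".

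The section does not say whether time is linear or categorical, where time zero lies, whether baseline is one of the modelled outcomes, or whether d is computed from the HLM. Baseline values are available: "All outcomes will be assessed at baseline, post-treatment, and 6-week follow-up" (section 4).

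**The concern.** Two visit-specific comparisons are promised, while the tests named are an intercept effect and a time effect. Depending on the coding, those two coefficients may not include a test at each visit. Separately, the reported effect size is baseline-adjusted but the hypothesis tests are not said to be. The p-values may then use the baseline information less efficiently than the estimates reported beside them. In a trial of 80 participants, that is precision given up although the data to supply it are already collected. Leaving the coding open also allows it to be chosen after the data are seen.

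**Working it through.** **The plan's own power figure.** Section 7 gives power .99 for 80 participants and a condition-by-time interaction of f = .25. The standard repeated-measures formula has noncentrality f² × N × m / (1 − rho), with m visits. Alpha .05 and rho are assumptions, because section 7 states neither.

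- m = 2, rho .5: .0625 × 80 × 2 / .5 = 20, power .993.
- m = 3, rho .5: .0625 × 80 × 3 / .5 = 30, power .999.
- m = 3, rho .3: .0625 × 80 × 3 / .7 = 21.4, power .989.

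The .99 is reproduced. It refers to a large difference, however. With m = 2, f = .25 is a between-arm difference in change of 4 × .25 = 1.0 SD. With m = 3 and an effect held at both follow-ups, it is .25 / √(1/18) = 1.06 SD at each. The .99 therefore does not carry over to a difference of 0.5 SD at one visit.

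**What the stated coefficients test, by coding.** Effects below are between-arm differences in SD units.

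1. *One linear time term, three equally spaced visits.* The slope over the whole period weights baseline, post-treatment and 6 weeks as (−1, 0, +1). At weeks 1, 7 and 12 of Table 1 the weights are (−1.03, +.06, +.97). The slope is in effect the 6-week change from baseline. The intercept is a baseline comparison if time starts there. Centred at post-treatment it is the three-visit mean: a true (0, .5, .5) gives (0 + .5 + .5)/3 = .33. Centred at 6 weeks it is a fitted value, .58, not the observed .5.
2. *The two follow-up visits only, one time origin.* With zero at post-treatment, the intercept tests post-treatment, and the time effect tests whether the arm difference changes by 6 weeks. For a maintained (.5, .5) that change is zero and the test rejects in 5% of trials, as it should; it is not a 6-week test. With zero at 6 weeks the roles reverse. Baseline is not used.
3. *Categorical time with baseline as reference.* Both visits are tested, as differences in change from baseline.

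**Precision at one visit.** Assumptions: 40 per arm (equal allocation is not stated), SD 1, the same correlation rho between all visits, complete normal data, two-sided .05, noncentral t. Standard errors:

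- change from baseline: √(2(1 − rho) × 2/40), 78 df
- unadjusted visit comparison: √(2/40), 78 df
- baseline as covariate: √((1 − rho²) × 2/40), 77 df

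| rho | SE change | SE unadjusted | SE adjusted | Power at d = 0.5 (change / unadjusted / adjusted) | Power at d = 0.3 |
|---|---|---|---|---|---|
| .3 | .265 | .224 | .213 | .46 / .60 / .64 | .20 / .26 / .28 |
| .5 | .224 | .224 | .194 | .60 / .60 / .72 | .26 / .26 / .33 |
| .7 | .173 | .224 | .160 | .81 / .60 / .87 | .40 / .26 / .46 |

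The adjusted variance is (1 + rho)/2 of the change variance (.65, .75, .85) and 1 − rho² of the unadjusted variance (.91, .75, .51). To match 40 per arm with adjustment, the change test needs 40 × 2/(1 + rho), about 62, 54 and 48 per arm. The unadjusted test needs 40/(1 − rho²), about 44, 54 and 79.

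**Cost of the linear reading when the effect does not last (rho .5).** If the effect is .5 at post-treatment and .25 at 6 weeks, the three-visit slope has power .20. If it is .5 and then 0, the slope has power .05. The adjusted post-treatment contrast has power .72 in both cases.

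**The case against.** The strongest reply is that the plan expressly commits to comparing conditions at both visits. Categorical time would do that, and so would fitting the model with time zero at each visit in turn. The power statement concerns a condition-by-time interaction, which fits categorical time at least as well as a linear slope. This stands. A reader might infer that the plan leaves one visit untested; the documents do not support that, because the gap appears only under some codings and the coding is unstated.

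Second, a reader might infer that the HLM tests ignore baseline. Where baseline is one of the modelled outcomes, the condition-by-time effect is a difference in change, which accounts for baseline and is valid. The shortfall there is precision. Only the follow-up-only reading leaves baseline unused.

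Third, a reader might infer that d and the p-value will often disagree. Simulation at d = 0.5 gave disagreement on significance in about 9% to 30% of trials, depending on rho and the comparison. Those rates require d to be adjusted by a baseline-covariate model and computed outside the HLM, and the plan states neither.

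Finally, this is a pilot: "Analyses will focus on size of treatment effects". The visit-specific adjusted d with its 95% interval already supports that purpose. No bias or inflated error rate follows from the present wording. These facts lower the severity. They do not remove the case for a more precise model that delivers the comparisons the plan says it wants.

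**Conclusion.** The point holds as a cheap improvement of low to moderate severity. The tests as worded do not guarantee a separate comparison at post-treatment and at 6 weeks, and they are not stated to use the baseline score as a covariate. On each of the three codings set out, a baseline-adjusted visit contrast has smaller variance than the corresponding change or unadjusted test. At a 0.5 SD effect the power gain ranges from small (.60 to .64 against the unadjusted test at rho .3; .81 to .87 against change at rho .7) to substantial (.60 to .87 against the unadjusted test at rho .7).

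The effect size, rho, equal allocation, complete normal data and compound symmetry are assumptions; none is in the documents. The figures do not carry over directly to yes/no sleep-aid use or to skewed outcomes such as percent heavy-drinking days. The planned d and its interval remain usable, and they could conflict with the HLM p-value only if computed outside the HLM.

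**What to change.** In the Aims 2-3 analyses of section 7, specify a mixed model with visit as a category, condition, condition-by-visit, and the baseline value of the outcome as covariate. An equivalent choice is to keep baseline among the modelled outcomes with the arm means constrained equal there. Make the condition contrasts at post-treatment and at 6 weeks the hypothesis tests, in place of the tests on the intercept and time effect. Take d and its 95% interval from those contrasts. For yes/no or strongly skewed outcomes, use the same two contrasts with a suitable link or distribution.

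The cost is a change of wording. The model is still an HLM and needs no further participants, visits or data. The downsides are a few more parameters, and low power at post-treatment if the effect builds gradually: about .25 for a 0.25 SD difference at rho .5, under the same assumptions.
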